7.4 Baseline Assessment Procedures

After completing study informed consent, participants will undergo a comprehensive evaluation to assess for inclusion and exclusion criteria. This will include self-reports and clinician assessments as shown in Table 1. This will also include assessment of depression severity and participants at highest risk for suicidality based on clinician assessment, those with a self-reported suicide attempt within the past year, and those felt likely to require hospitalization during the course of the study will be excluded. The comprehensive exam will also include a history and physical exam by the study PI (pulse oximetry measurements will be a component of the respiratory evaluation) and baseline medication evaluation for potential harmful interactions. Urine pregnancy tests will be completed for every woman of childbearing potential. Urine drug screening will be collected at baseline and prior to each ketamine session to monitor

for opioid and other illicit substance use. For patients currently taking methadone, ECG will be performed to assess for cardiac function with QTc interval of 450ms or longer being exclusionary. Assessments may be conducted by telehealth with vital signs to be provided by participant's home or pharmacy measurement.

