5.3 Exclusion Criteria

Subjects will be excluded from the study if any of the following criteria apply:

1. They are considered an immediate suicide risk by clinician assessment, self-report a suicide attempt within the past year or felt to be likely to require hospitalization during the study.
2. Subjects who meet DSM-5 criteria for current bipolar disorder based on clinical interview.
3. Subjects who meet DSM-5 criteria for current or history of psychotic spectrum disorders based on clinical interview.
4. Subjects meeting DSM-5 criteria for current substance use disorder (*i.e.*, not in early or sustained remission) other than tobacco use disorder.
5. Subjects who report use of ketamine >20 times in the past or who meet DSM-5 criteria for Other Hallucinogen Use Disorder due to ketamine use including subjects who are currently in early or sustained remission.
6. Women who are pregnant or nursing, and women who do not consent to use methods of highly effective birth control during the interventional phase of the study.
7. Subjects with hypertension as defined by a baseline visit systolic blood pressure (SBP) >140 mmHg or a diastolic blood pressure (DBP) >90 mmHg.
8. A history of allergic or other adverse reaction to ketamine (or its excipients).
9. Clinically significant physical exam findings or self-reported medical conditions for which a transient increase in blood pressure could be significantly detrimental (e.g. glaucoma, aneurysmal disease, cardiovascular disease, or end-stage renal disease).
10. QTc will be measured in subjects currently taking methadone and those with QTc 450ms or longer will be excluded.
11. Subjects who live greater than 20 miles from the study site and cannot arrange their own transportation will be excluded from the study.
12. Subjects with clinically significant kidney or liver impairment.

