7.3 Schedule of Assessments

The instruments to be used are standardized, have good psychometric properties, and are widely used. The schedule of study assessments is provided in **Table 1**.

Table 1: Schedule of Assessments

Instrument Name	Purpose	TIME POINT		
		BL (Wk 0)	Tx 1-8 (Wk 1-8)	Follow-up (Wk 9, 10, 12, 16)
Self-Reports and Consents				
Informed Consent	Obtain informed consent	X		
Demographics Form	Sample characterization	X		
Beck Depression Inventory-II	Self-reported assessment of depression symptom severity	X	X	X
Visual Analog Scale (VAS)	Measure subjective levels of opioid craving	X	X	X
General Anxiety Disorder (GAD-7)	Self-report of anxiety symptom severity	X	X	X
Mystical Experiences Questionnaire (MEQ)	Measure of perceptual experiences		X	
Brief Pain Inventory	Measure of pain and quality of life	X	X	X
Insomnia Severity Index (ISI)	Assess insomnia and sleep quality	X	X	X
Five Facets of Mindfulness (FFMQ)	Assess aspects of mindfulness related	X	X	X
PTSD Checklist (PCL-5)	Measure of PTSD symptoms	X	X	X
Fagerstrom Test of Nicotine Dependence (FTND)	Measure of nicotine dependence	X	X	X
Timeline Follow-Back (TLFB)	Measure of substance use	X	X	X
Clinician Assessments				
History and Physical Exam	Eligibility assessment	X		
Vital Signs Measurement	Obtain readings of blood pressure, pulse, temperature, respirations and pulse oximetry	X	X*	
Montgomery-Asberg Depression Rating Scale (MADRS)	Primary Outcome: Clinician assessed measure of depression symptom severity	X	X	X
Pre-screening Questionnaire	To assess for basic eligibility criteria before completing a full baseline visit.	X		
Laboratory and Procedural Tests				
Urine Pregnancy Test (female subjects only)	Eligibility assessment	X	X	
Urine Drug Screen	Assessment of illicit drug use	X	X	
Electrocardiogram (ECG; subjects on methadone only)	Assessment of cardiac function	X		

* Vital signs (blood pressure, pulse, respiratory rate, and pulse oximetry) will be obtained prior to treatment sessions and at 60 minutes post-treatment. Temperature will be monitored immediately prior to treatment. If there is an increase in systolic or diastolic blood pressure >30 mm Hg from baseline, or an increase in pulse rate >30 bpm from baseline, subjects will be treated with standard of care antihypertensive medications (i.e. clonidine) and the measurements will be repeated every 20 minutes until BP and pulse are within 30 points of the baseline values.

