7.5 Intervention Visit Procedures

Prior to administration of the study compounds, participants will complete self-report questionnaires and clinical assessments. The study physician will disinfect the subject's shoulder using an alcohol wipe, and the study physician will then administer the medication by intramuscular administration into the participant's deltoid muscle. Vital signs will be monitored prior to treatment, and at 60 minutes post-treatment. If during the post-administration observation period, ketamine administration causes an increase in systolic or diastolic blood pressure >30 mm Hg from baseline, or an increase in pulse rate >30 bpm from baseline, the subject will be treated with standard of care antihypertensives (i.e. clonidine), and repeat vital sign measurements will be taken approximately every 20 minutes until blood pressure and pulse are within 30 points of baseline values. Standard of care antihypertensive medications will be procured via intrainstitutional transfer from MUSC investigational drug services pharmacy distribution center. They will be stored in a DHEC compliant locked box within a locked room accessible only to study team members. If the subject experiences symptoms of hypertensive emergency, the subject will not receive further administration of ketamine and will be withdrawn from the study. After completion of the injection, participants until returned to baseline per clinical assessment which time they will undergo debriefing and complete assessments of their perceptual experience of the intervention. We will evaluate the effects of a weekly interventions for 8 sessions. Participants will return for follow-up assessment 1, 2, 4 and 8 weeks following final medication session. Follow-up visits may be conducted by telehealth.

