9.0 PROVISIONS TO MONITOR THE DATA TO ENSURE THE SAFETY OF SUBJECTS

Ongoing Clinical Monitoring: The research team will closely monitor for any increase in substance use or psychiatric distress at every study intervention visit. Subjects with clinically significant worsening of depression (i.e. development of suicidal ideation) or worsening of opioid use will be immediately referred for a higher level of treatment, and the PI will review trial safety. The PI will be responsible for assessing potential participants for inclusion and exclusion criteria, and for assessing for adverse effects (AE's) throughout the trial. AE's will be collected, documented, and reported. If the AE is not serious, the information will be recorded, managed medically as appropriate, and the event will be followed until resolution. SAEs will also be recorded on the AE Form, managed medically as appropriate, and the event is followed until resolution. In addition, the PI will review all completed AE forms for determination of SAE. All SAE reports will be sent to the MUSC IRB within 24 hours of learning of event occurrence. The PI will be responsible for withdrawal of a study participant if they become pregnant or feel that participation is no longer in a subject's best interests. Mental health symptoms will be monitored using standardized measures at each visit in order to detect any worsening symptoms. Additionally, participants will be advised to observe any signs of worsening substance use or depression symptoms, and to discuss these with the research team. All participants will be informed at the initial visit that they may terminate participation at any point. If a participant experiences distress or other problems between visits, he or she will be encouraged to contact [name] or his/her outpatient mental health provider. If a participant needs or desires immediate attention, arrangements will be made for an appointment with an experienced mental health provider. The informed consent document will provide direction to contact the study staff during office hours and/or go to the Emergency Room at any time for worsening of symptoms. In addition, participants will have access to urgent care services at MUSC. If any of the research personnel believes that a participant is medically or psychiatrically compromised by participation, the PI will be notified and will contact the participant immediately to assess concerns and assure participant safety. The PI will attempt to address all participant concerns and will set up an alternate referral for counseling for those who desire it from outside the project. All participants will review, at the initiation of participation, an informed consent document which specifically reviews potential psychological distress as a potential outcome of participation. If necessary, the participant will be asked to complete a safety plan and to call the project staff, a national hotline, or 911. The Mobile Crisis unit of Charleston County, which involves a team of police and psychiatric workers, or the EMS unit may be dispatched to the participant's home to assure safety. The investigative team has a long history of ensuring participant safety using similar methods in these populations.

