10.0 WITHDRAWAL OF SUBJECTS

All potential participants will be thoroughly screened for eligibility after completing informed consent. The PI may withdraw subjects from participation at any time if the participant demonstrates or reports significant distress, is felt to be at risk of harm to themselves or to others, or is otherwise unable to complete the study protocol. Referrals to university and community resources will be made as indicated for all participants withdrawn from the study. The trial will be stopped under any of the following conditions: 1) there is clear evidence of harm; 2) there is no likelihood of the intervention demonstrating benefit, or 3) there is overwhelming evidence of the benefit of the intervention.

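### Remote screening lets the blood-pressure exclusion rest on a home or pharmacy reading, with no recheck against the limit before the first dose

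*Combined protocol and SAP*

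**What the plan says.** Section 5.3 of the combined protocol and SAP defines the seventh exclusion as "Subjects with hypertension as defined by a baseline visit systolic blood pressure (SBP) >140 mmHg or a diastolic blood pressure (DBP) >90 mmHg". The definition is tied to one visit.

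Section 7.4, on the baseline assessment, ends with this permission: "Assessments may be conducted by telehealth with vital signs to be provided by participant's home or pharmacy measurement". It does not specify a device, a number of readings, how recent the value must be, or any confirmation on site.

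At treatment visits, the footnote to Table 1 (section 7.3) says: "Vital signs (blood pressure, pulse, respiratory rate, and pulse oximetry) will be obtained prior to treatment sessions and at 60 minutes post-treatment". Section 7.5 repeats this: "Vital signs will be monitored prior to treatment, and at 60 minutes post-treatment". Neither gives a pre-dose value above which the injection is withheld.

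The one pressure-related stopping rule, also in section 7.5, is: "If the subject experiences symptoms of hypertensive emergency, the subject will not receive further administration of ketamine and will be withdrawn from the study".

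**The concern.** Section 11.2 ranks a short-lived pressure rise as ketamine's leading physical risk, and the sponsor chose 140/90 as the entry limit. That limit protects a participant only as well as the reading it is applied to. Under the telehealth permission, the reading may come from equipment and conditions the study team does not control.

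The first pressure taken under study conditions may then be the one before the first injection. If it is above 140/90, the protocol does not say the person is ineligible or that the dose must be withheld. At stake is participant safety at the first dose, and whether a stated exclusion is enforced. The efficacy outcome and its analysis are not touched.

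**Working it through.** The plan gives no figure to reproduce, so the check sets its blood-pressure provisions side by side.

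| Provision | Reading it applies to | Limit | Consequence |
|---|---|---|---|
| 5.3, exclusion 7 | Baseline visit | SBP >140 or DBP >90 | Excluded |
| 7.4, telehealth sentence | Baseline, home or pharmacy value allowed | None added | None |
| Table 1 and 7.5, pre-dose vital signs | Before each session | None | None stated |
| Table 1, 7.5 and 11.2, rise rule | Change from baseline; in 7.5, after dosing | >30 mmHg | Antihypertensive treatment; 7.3 and 7.5 add repeat readings about every 20 minutes |
| 11.2, absolute rule | Not tied to a pre-dose check | >180 SBP or >105 DBP | Antihypertensive treatment and monitoring |
| 7.5, stopping rule | Symptoms | Hypertensive emergency | No further ketamine; withdrawn |

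1. *The telehealth sentence concerns baseline.* Table 1 schedules vital signs at baseline and at treatment visits 1 to 8, with none at follow-up. Treatment visits involve an injection on site. Baseline is the only visit at which a remote vital sign could be used.

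2. *Nothing carries 140/90 forward.* The limit appears once, in 5.3. The thirty-day window in 5.2 governs the inclusion criteria only. Section 7.1 has participants already judged eligible return for the first ketamine session.

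3. *The other triggers do not substitute for it.* Take a hypothetical participant with a remote reading of 140/90, which is not excluded, and a pre-dose reading of 150/95. The rise is 150 − 140 = 10 systolic and 95 − 90 = 5 diastolic, well short of 30. The value is also below 180/105. No written rule is triggered and the injection can proceed.

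4. *What the entry limit does.* Section 11.2 quotes mean rises of 19.6 systolic (± 12.8) and 13.4 diastolic (± 9.8).
   - From 140/90: 140 + 19.6 = 159.6 and 90 + 13.4 = 103.4, both below the 180/105 trigger.
   - From a diastolic of 92: 92 + 13.4 = 105.4, above 105.
   - From 150/95: 150 + 19.6 = 169.6 and 95 + 13.4 = 108.4, so the diastolic trigger is passed.

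   This illustrates how little diastolic margin remains above the limit. It is not a risk estimate: the means come from earlier studies, section 11.1 describes the evidence base as intravenous, and individuals vary widely.

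5. *Number affected.* The documents do not say how many baselines will be remote or how remote readings differ from study readings. The range is 0 to about 10, the planned enrollment in section 5.4.

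**The case against.** The best counter-argument is that the gap is not peculiar to remote screening. Exclusion 7 uses the baseline reading for everyone, and a person screened on site who reads 150/95 on the first dosing day could also be dosed without a deviation. A recheck for remote participants alone might then seem to impose a second standard on them, when nothing in the documents shows that home or pharmacy readings are worse. The first part is true. But someone screened on site has met the limit once on a reading taken at the study visit; a remotely screened person may never have done so. Confirming the remote value gives both groups one verified qualifying reading.

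Other text suggests that wholly remote baselines may be rare. Section 5.5 places procedures on campus, section 6.2 puts consent at the research offices, and section 7.4 includes a physical examination by the PI and urine tests. This could bring the number affected down to zero. It does not cancel the specific permission about vital signs, and none of it requires a confirmatory pressure.

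There are real safeguards. A physician gives each dose ("the study physician will then administer the medication by intramuscular administration"), and a pre-dose reading would be available. Section 9.0 states: "The PI will be responsible for assessing potential participants for inclusion and exclusion criteria". Section 10.0 adds: "The PI may withdraw subjects from participation at any time". Exclusion 9 removes people with conditions that a pressure rise could seriously harm, monitoring is continuous until recovery, and section 11.2 provides two hours of observation. These lower the chance of harm, and many physicians would withhold the dose. None sets a pressure at which the first dose may not be given.

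Finally, the protocol does not say who takes the pre-dose reading. Calling it a staff reading is an inference from Table 1, which lists vital signs under clinician assessments.

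**Conclusion.** The concern holds. For a participant whose baseline vital signs were remote, exclusion 7 can be satisfied by a reading the study team did not take or verify, and no text applies the limit again before the first dose. The protocol should be changed, but this does not undermine the study. What is missing is a written threshold, not a measurement.

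Confidence is high on what the text says and omits. The consequence cannot be sized: no excess risk can be derived, and 0 to about 10 participants could be affected. The conclusion assumes that the telehealth sentence permits what it says despite the general on-campus statement, and that study personnel take the pre-dose reading. It is limited to eligibility at the first dose.

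**What to change.** Add to sections 5.3 and 7.4 that, when baseline vital signs were obtained remotely, exclusion 7 must be confirmed on the pre-dose reading taken by study personnel at the first treatment visit. Allow one repeat after a rest period. If systolic pressure is still above 140 or diastolic above 90, ketamine is not given.

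The cost is one or two sentences and at most one repeat reading. No scheduled measurement is added, because Table 1 already includes this one, and telehealth screening is kept. The downside is an occasional late screen failure. Each would be 1/10 = 10% of planned enrollment unless replaced, and the rest-and-repeat step limits how often a passing high reading causes one.

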7.5 Intervention Visit Procedures

Prior to administration of the study compounds, participants will complete self-report questionnaires and clinical assessments. The study physician will disinfect the subject's shoulder using an alcohol wipe, and the study physician will then administer the medication by intramuscular administration into the participant's deltoid muscle. Vital signs will be monitored prior to treatment, and at 60 minutes post-treatment. If during the post-administration observation period, ketamine administration causes an increase in systolic or diastolic blood pressure >30 mm Hg from baseline, or an increase in pulse rate >30 bpm from baseline, the subject will be treated with standard of care antihypertensives (i.e. clonidine), and repeat vital sign measurements will be taken approximately every 20 minutes until blood pressure and pulse are within 30 points of baseline values. Standard of care antihypertensive medications will be procured via intrainstitutional transfer from MUSC investigational drug services pharmacy distribution center. They will be stored in a DHEC compliant locked box within a locked room accessible only to study team members. If the subject experiences symptoms of hypertensive emergency, the subject will not receive further administration of ketamine and will be withdrawn from the study. After completion of the injection, participants until returned to baseline per clinical assessment which time they will undergo debriefing and complete assessments of their perceptual experience of the intervention. We will evaluate the effects of a weekly interventions for 8 sessions. Participants will return for follow-up assessment 1, 2, 4 and 8 weeks following final medication session. Follow-up visits may be conducted by telehealth.

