11.2 Physical Risks

The most significant physical adverse event from ketamine is a transient increase in blood pressure, which in previous studies was experienced by 29.8% of subjects with a mean systolic blood pressure increase of 19.6 mmHg +/- 12.8 mmHg and a mean diastolic blood pressure increase of 13.4 mmHg +/- 9.8 mmHg. Peak levels are reached on average 40 minutes post-treatment and resolve by 240 minutes post-treatment (Wan et al., 2015). Participants experiencing clinically significant hypertension (greater than 180 mmHg SBP or greater than 105 mmHg DBP, or greater than 30 mmHg SBP or DBP from baseline values) will be treated with standard of care hypertensives (e.g. clonidine) and monitored until symptom resolution.

The most prevalent physical adverse effect was transient sedation and occurs in approximately 16% of patients receiving ketamine. Sedation will be monitored via continuous clinical observation during interventional sessions. A medical emergency team will be called for participants that are unable to be aroused with painful trapezius squeeze or that experience hypoxia (i.e. a pulse oximeter reading of 92% or less), although in the investigative team's extensive experience using ketamine clinically for depression at these doses, such serious events have never occurred. Vital signs will be routinely monitored during treatment and emergency airway equipment will be immediately available. Subjects will be monitored for 2 hours post-dose by trained healthcare professionals (eg PI, co-I, or study nurse). Due to transient cognitive impairment associated with sedation, participants will not be allowed to drive themselves following the interventions. Subjects who do not have transportation and live within 20 miles will receive compensation for taxi, Uber or Lyft transportation to and from medication sessions up to \$100 each way. Subjects who live greater than 20 miles from the study site and cannot arrange their own transportation will be excluded from the study. Participants will be advised not to operate heavy machinery for at least 24 hours after the interventions.

There are also the standard risks associated with intramuscular injections including temporary local pain, irritation, or redness at the site of the injection. There is a very small (<1%) risk of infection, muscle fibrosis, or persistent muscle or nerve damage at the site of injection.

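### The only timed post-dose vital signs come at 60 minutes, after the cited blood-pressure peak, and the 7.3/7.5 treatment trigger leaves out the diastolic limit of 105 mmHg in 11.2

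*Combined protocol and SAP*

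**What the plan says.** **Timing.** Section 7.5 states "Vital signs will be monitored prior to treatment, and at 60 minutes post-treatment". The Table 1 footnote in 7.3 says the same and names the measures: "Vital signs (blood pressure, pulse, respiratory rate, and pulse oximetry) will be obtained prior to treatment sessions and at 60 minutes post-treatment". Section 11.2 says of blood pressure: "Peak levels are reached on average 40 minutes post-treatment and resolve by 240 minutes post-treatment". Section 11.1 describes the evidence behind these figures as intravenous. Section 3.3 puts the drug peak after intramuscular injection, the route used here, at 5 to 30 minutes.

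**Treatment trigger.** The Table 1 footnote acts on a relative change: "If there is an increase in systolic or diastolic blood pressure >30 mm Hg from baseline". Section 7.5 uses the same threshold ("If during the post-administration observation period, ketamine administration causes an increase in systolic or diastolic blood pressure >30 mm Hg from baseline") and adds pulse ("an increase in pulse rate >30 bpm from baseline"), as does the footnote. Section 11.2 also acts on a rise above 30 mmHg, but adds two absolute limits, systolic above 180 and diastolic above 105. It has no pulse trigger.

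**Ending the repeats.** Once the trigger is met, the footnote says "measurements will be repeated every 20 minutes until BP and pulse are within 30 points of the baseline values", and 7.5 agrees. Section 11.2 instead monitors until symptoms resolve.

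**Reference value.** No section says whether baseline means the baseline visit or the reading before each session. For the baseline visit, 7.4 says "Assessments may be conducted by telehealth with vital signs to be provided by" the participant's home or pharmacy measurement. Section 5.3 excludes anyone above 140 systolic or 90 diastolic at that visit. No pre-dose limit is set for the eight weekly sessions.

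**General monitoring.** Section 9 promises continuous medical and psychiatric monitoring until the participant has recovered. Section 11.2 promises routine vital signs during treatment and two hours of observation after the dose. Neither gives a measurement time or interval.

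**The concern.** Section 11.2 names a transient rise in blood pressure as the most significant physical adverse event, and tolerability is Specific Aim 2. Section 3.3 raises the dose in 0.25 mg/kg steps according to tolerability, which it does not define. If blood pressure counts towards tolerability, the only timed reading available for the next dose decision is taken after the expected peak. Section 7.5 applies its trigger throughout post-dose observation, but schedules no reading in the first hour with which to apply it. The 20-minute repeats do not fill that hour, because they begin only after the trigger is met. Oximetry has the same gap: 11.2 calls an emergency team at a saturation of 92% or less, yet no oximetry time is set before 60 minutes.

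The trigger is a second, separate matter. Staff working from Table 1 and 7.5 would not see the absolute limits in 11.2. They could leave untreated a diastolic pressure that 11.2 says to treat, and could end the repeats while it was still above that limit.

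**Working it through.** The plan states no figure to reproduce here. The check compares the sections and does threshold arithmetic.

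**Timing.** Inputs: timed reading at 60 minutes (7.3, 7.5); average blood-pressure peak at 40 minutes (11.2); intramuscular drug peak at 5 to 30 minutes (3.3).

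- Lag behind the cited blood-pressure peak: 60 − 40 = 20 minutes.
- Lag behind the intramuscular drug peak: 60 − 30 = 30 to 60 − 5 = 55 minutes.

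**How far a rise could fall back by 60 minutes.** The documents give no intramuscular blood-pressure course, so the shape of the fall is an assumption. If a fraction f of the peak rise remains at 60 minutes, a peak rise between 30 and 30/f mmHg reads at or below the trigger.

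- Straight-line fall from 40 minutes to zero at 240 minutes: f = 1 − 20/200 = 0.90, and 30/0.90 = 33.3 mmHg.
- Peak at 40 minutes, halving every 60 minutes: f = 0.794, and 30/0.794 = 37.8 mmHg.
- Peak at 40 minutes, halving every 30 minutes: f = 0.630, and 30/0.630 = 47.6 mmHg.
- Straight-line fall to 240 minutes with the peak at 30 or at 5 minutes: f = 0.857 or 0.766, giving 35.0 or 39.2 mmHg.

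The hidden band therefore runs from 30 to somewhere between about 33 and 48 mmHg, depending wholly on the assumption. Untimed readings could still catch such a rise.

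**Diastolic limit.** The relative rule acts above baseline + 30; the 11.2 limit acts above 105. They coincide at a baseline of 105 − 30 = 75. Above that, the 11.2 limit is reached first.

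| Baseline diastolic | Rise that passes 105 | 7.3/7.5 acts above | Above the 11.2 limit but not covered by 7.3/7.5 |
|---|---|---|---|
| 80 | more than 105 − 80 = 25 | 110 | up to 5 mmHg |
| 85 | more than 105 − 85 = 20 | 115 | up to 10 mmHg |
| 90 | more than 105 − 90 = 15 | 120 | up to 15 mmHg |

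At a baseline of 90, the 15 mmHg mark is 15 − 13.4 = 1.6 mmHg above the mean diastolic rise cited in 11.2. The text leaves unclear whether that mean covers all participants or only the 29.8% who had a rise, so this gives only an idea of scale.

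**Systolic limit.** The rules coincide at 180 − 30 = 150. At the entry ceiling of 140, the relative rule acts above 140 + 30 = 170, before 180 is reached. The 180 limit adds protection only if the reference is above 150, for example a pre-dose value of 155, where the relative rule would wait until above 185.

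**Ending the repeats.** Being within 30 points of a baseline diastolic of 90 is satisfied at 120, which is 120 − 105 = 15 mmHg above the level at which 11.2 calls for treatment.

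**The case against.** The strongest reply is that the protocol must be read as a whole. Section 9 promises continuous monitoring, 11.2 promises routine vital signs and two hours of observation, and the 7.5 trigger covers the full observation period. On that reading 60 minutes is a minimum, and only an interval is missing. Section 11.2 also remains in force, so a team that knows the whole document would treat a diastolic pressure above 105. Much of this stands. A reader might infer that blood pressure goes unmeasured for the first hour, or that the sections contradict each other; the text supports neither. Earlier readings may well be taken, and the two trigger lists differ only by omission. What remains is that no section requires a reading at any stated time near the peak.

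The peak comparison is also imperfect. The 40 minutes is intravenous, and the 5 to 30 minutes is a drug peak, not a pressure peak. A rise that is back within 30 mmHg by 60 minutes already meets the plan's own rule for ending repeats. What may be lost is treatment near the peak and a record of it. It would be tempting to quote a share of rises missed, but the documents cannot support one.

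A reader might also give the missing systolic limit the same weight as the diastolic one. Against the baseline visit it adds nothing, since 170 comes before 180. It matters only if the reference is a later pre-dose value above 150, which no per-session limit rules out.

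Other safeguards count too. Section 5.3 excludes conditions, including cardiovascular and aneurysmal disease, in which a pressure rise could do serious harm. The 60 mg daily cap limits escalation: for an assumed weight of 80 kg it is 60/80 = 0.75 mg/kg, one step above the starting dose.

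**Conclusion.** The point holds as a low-cost safety improvement with two parts. First, the only timed post-dose blood pressure, pulse and oximetry reading comes 20 minutes after the cited average pressure peak and 30 to 55 minutes after the intramuscular drug peak. A rise above the trigger near the peak can, but need not, go unmeasured. How often is unknown, because it depends on an intramuscular time course that the documents do not give and on how the untimed monitoring is carried out.

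Second, the 7.3/7.5 trigger and its rule for ending repeats omit the diastolic limit of 105. For any baseline diastolic above 75 there is a range above 105 that they do not cover, up to 15 mmHg wide at a baseline of 90. This part is plain arithmetic and needs no model. Its practical effect depends on staff working from 7.3 and 7.5 without 11.2. The point concerns when repeat measurements end, not the separate symptom-based rule in 7.5 for withdrawing a participant.

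The MADRS outcome is unaffected and no blood-pressure endpoint is planned.

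**What to change.** - In the Table 1 footnote and 7.5, add timed blood pressure, pulse and oximetry readings at about 20 and 40 minutes, and keep the one at 60.
- Use one trigger set in 7.3, 7.5 and 11.2: a rise of more than 30 mmHg systolic or diastolic, or of more than 30 bpm in pulse; or diastolic above 105; or systolic above 180.
- Measure rises from the lower of the baseline-visit and session pre-dose values. Using the pre-dose value alone could loosen the rule: with 140 at the baseline visit and 155 before the session, the combined set would act above 180 instead of above 170.
- Continue the 20-minute repeats until no trigger is met.
- State observation as at least two hours and until return to baseline.
- Say what happens when a pre-dose value already meets a trigger, since no per-session limit exists now.

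The cost is protocol wording plus two sets of readings per session by staff already present. For about 10 participants and 8 sessions that is 10 × 8 × 2 = 160 sets at most, with no new equipment or visits. The drawbacks are brief interruptions of the therapy session during acute drug effects and possibly a few more antihypertensive treatments.
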